- Title, Sections 1.2, 1.3, 2, 3.1, 3.3.2, 3.3.5, 4.1, 4.1.1, and 6.4.1, Figure 2, and Figure 3 were updated to clarify the terminology related to characterization of the eligible patient population. The term “intermediate or high probability” of Group 3 pulmonary hypertension reflects the 2015 European Society of Cardiology (ESC)/ European Respiratory Society (ERS) guideline and it is related to echocardiography assessments. As in this study, the patients are eligible based on right heart catheterization (RHC) or ECHO data, the terminology “risk of Group 3 pulmonary hypertension” is considered more appropriate. Hence throughout the protocol, when describing the eligible population “intermediate or high probability” of Group 3 pulmonary hypertension was changed to “risk” of Group 3 pulmonary hypertension.
- Section 1.3 was updated to include collection from randomized patients of the most recent high-resolution computed tomography (HRCT) scans performed prior to entering the study. Following availability of data from the RISE-IIP study (Nathan et al 2016, ERS) which showed an increased incidence of death both from the main study and the open-label extension period, the intention is to collect HRCT from randomized patients to support, if considered necessary, an in-depth analysis of any case of death in the current study. Moreover in view of the fact that results from RHC which allows to characterize the severity of pulmonary vascular disease will be available only in small proportion of patients (majority of the patients so far being eligible are based on ECHO data), having the possibility to potentially evaluate baseline HRCT for signs of pulmonary vascular disease might be considered relevant for the study.
- Section 3.1 was updated to include clarification to the text that the washout period can be part of the Run-in period, if the Run-in period is applicable. In the protocol version 1, this text was provided only as a footnote to Figure 1. This has been added now also to the text.
- Section 3.1 was updated to include also region Asia-Pacific, as potentially, additional countries might join the study.
- Sections 3.1, 3.2, and Figure 1 have been clarified in the protocol that the study ends when all patients complete the overall 12 months safety follow-up period, i.e. 4 weeks follow-up after end of treatment at week 52 plus additional 11 months safety follow-up after the Follow up visit at week 56. Thus, depending on the

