28/Protocol MA29957, Version 2

Statistical Methods

Primary Analysis

The primary efficacy objective for this study is to evaluate the efficacy of adding sildenafil compared with placebo to pirfenidone treatment on disease progression. The primary endpoint will be evaluated based on a comparison of the proportion of patients showing disease progression over 52 weeks of treatment period, as evidenced by reaching the following combined endpoint:

- Relevant decline in 6MWD of at least 15% from baseline (as defined below*), respiratory-related non-elective hospitalization, or all-cause mortality

* Relevant decline in 6MWD from baseline is further specified as:

- Any decline >25% from baseline or
- A decline between 15-25% from baseline, if accompanied by at least one of the following:
 - worsening of SpO₂ desaturation during the 6MWT compared to baseline
 - worsening of the maximum Borg scale during the 6MWT compared to baseline
 - increased O₂ requirements during the 6MWT compared to baseline.

The primary analysis will be based on the Intent-to-treat (ITT) population, defined as all randomized patients. Patients who discontinue treatment prematurely will be analyzed based on the available data. No imputation method will be applied. Patients who undergo lung transplantation during the study will be withdrawn from the study at the time of hospitalization for transplantation. *In addition, sensitivity analysis of the primary endpoint will be performed. The details of those sensitivity analyses will be provided in the Statistical Analysis Plan.* The primary analysis of the primary endpoint will compare disease progression rates in each treatment arm using a Chi-square test with a one-sided significance level $\alpha = 0.05$.

Determination of Sample Size

There are no reference data available on the use of pirfenidone in this patient population with a measurable DLCO $\leq 40\%$ of predicated value and mPAP ≥ 20 mmHg on RHC. A total sample size of approximately 176 patients is planned, and patients will be randomized 1:1 to the two treatment groups. The statistical hypothesis for the treatment comparison is based on the proportion of patients who experienced a $\geq 15\%$ decline from baseline in 6MWD, were hospitalized for cardiac- or respiratory non-elective reasons, or who died, according to a pooled analysis of the effects observed in the pirfenidone groups of three large Phase III trials (CAPACITY 1, CAPACITY 2, and ASCEND).

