The randomization will be stratified by previous RHC availability for inclusion (yes/no) and by degree of pulmonary function measured by forced expiratory volume in 1 second (FEV1)/FVC ratio below/above 0.8.

Patients will have a total of up to approximately 12 to 13 clinic visits, including one or more visits during the Washout and Screening Periods, up to 10 Treatment Period visits, and one Follow-up visit (see [Figure 1](#)).

Figure 1 Study Schema

ICF = Informed Consent Form

* Patients will be required to discontinue all prohibited medications and undergo a 28-day Washout Period prior to entering the study. Patients not taking a prohibited medication will directly enter Screening. A prior run-in period will be provided for countries where patients will not be able to take pirfenidone for 12 weeks due to reimbursement issues. The run-in period can include the Washout period (if applicable).

** After the completion of the treatment period (Visit 10) and 4 weeks safety follow-up, the possibility will be offered to the patients to receive pirfenidone within the study protocol up to 11 months safety follow-up.

In addition, the sponsor will offer the possibility to the patients to receive pirfenidone within the study protocol after the Follow-up visit at week 56 for up to 11 months safety

Pirfenidone and sildenafil—F. Hoffmann-La Roche Ltd
43/Protocol MA29957, Version 2

follow-up. During this time, the patients should be evaluated by the treating physician approximately every three months.

A patient diary will be used to record adverse events, daily dosing adherence for both pirfenidone and sildenafil/placebo, and concomitant medication use from the Screening visit until the Follow-up visit. Also, patients will receive a wallet card that provides important information relevant to study participation.

During the study, assessments will be performed according to the Schedule of Assessments ([Appendix 1](#)).

An iDMC will be established to monitor the progress of the study and ensure that the safety of patients enrolled in the study is not compromised. The iDMC may recommend that the Sponsor stop the study for safety concerns.

A detailed description of the procedures, data flow and the meeting schedule of the iDMC will be maintained in a separate iDMC Charter, by the Sponsor and the iDMC.

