3.3.6 Rationale for Choice of Stratification Factors

The randomization will be stratified by availability of a previous RHC (yes/no) and by FEV1/FVC ratio below/above 0.8, to ensure an equal distribution of patients with some degree of pulmonary obstruction in both treatment groups. Stratified randomization is included as the treatment outcome may be affected by these factors.

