4.2 METHOD OF TREATMENT ASSIGNMENT AND BLINDING

Patients will be randomized 1:1 to receive either pirfenidone plus sildenafil or pirfenidone plus placebo. The randomization process will be conducted using a validated interactive voice or web-based response system (IxRS). To guard against systematic selection bias and ensure comparability of treatment groups, the randomization will be stratified by availability of a previous RHC (yes/no) and by FEV1/FVC ratio below/above 0.8 to ensure an equal distribution of patients with some degree of pulmonary obstruction in both treatment groups.

To maintain the double-blind nature of the study, the sildenafil and placebo treatments will be identical in appearance (see [Section 4.3.1.2](#)).

The investigational site personnel and the patients will be blinded to treatment assignment from randomization onwards. The iDMC and any personnel performing interim analysis (as applicable) will be unblinded to treatment throughout the study.

If unblinding is necessary for patient management (e.g., in the case of a SAE for which patient management might be affected by knowledge of treatment assignment), the Investigator will be able to break the treatment code by contacting the IxRS. Treatment codes should not be broken except in emergency situations. If the Investigator wishes to know the identity of the study drug for any other reason, he or she should contact the Medical Monitor directly. The Investigator should document and provide an explanation for any premature unblinding (e.g., accidental unblinding, unblinding due to a SAE).

For regulatory reporting purposes, and if required by local health authorities, the Sponsor will break the treatment code for all serious, unexpected suspected adverse reactions (see [Section 5.7](#)) that are considered by the Investigator or Sponsor to be related to study drug.

Unblinding should not necessarily result in the withdrawal of a patient from the study. Every effort should be made to retain unblinded patients in the study.

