6.4.1 Primary Efficacy Endpoint

The primary efficacy objective for this study is to evaluate the efficacy of adding sildenafil compared with placebo to pirfenidone treatment in patients with advanced IPF and *risk* of Group 3 PH.

The primary efficacy endpoint will be evaluated based on a comparison of the proportion of patients showing disease progression over 52 weeks of treatment period, as evidenced by reaching the following combined endpoint:

- Relative decline in 6MWD of at least 15% from baseline (as defined below*), respiratory-related non-elective hospitalization, or all-cause mortality

* Relevant decline in 6MWD from baseline is defined as:

- Any decline >25% from baseline or
- A decline between 15-25% from baseline, if accompanied by at least one of the following:
 - worsening of SpO₂ desaturation during the 6MWT compared to baseline

- worsening of the maximum Borg scale during the 6MWT compared to baseline
- increased O₂ requirements during the 6MWT compared to baseline.

The primary analysis will be based on the ITT population, defined as all randomized patients. Patients who discontinue treatment prematurely will be analyzed based on the available data. No imputation method will be applied. Patients who undergo lung transplantation during the study will be withdrawn from the study at the time of hospitalization for transplantation. *In addition, sensitivity analysis of the primary endpoint will be performed. The details of those analyses will be provided in the Statistical Analysis Plan.*

The primary analysis of the primary endpoint will compare disease progression rates in each treatment arm using a Chi-square test with a one-sided significance level $\alpha = 0.05$.

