- Dyspnea as assessed by the UCSD SOBQ will be summarized descriptively over time. The change from baseline will be compared between the treatment arms using a rank ANCOVA with change from baseline as outcome variable and standardized rank baseline value as covariate.
- HRQoL assessed by SGRQ will be summarized descriptively over time. The change from baseline will be compared between the treatment arms using a rank ANCOVA with change from baseline as outcome variable and standardized rank baseline value as covariate.
- Changes from baseline in NT-proBNP levels will be summarized descriptively over time.

For all secondary endpoints p-values will be reported in a descriptive fashion. No multiplicity adjustments for statistical testing will be done.

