6.4.3 Exploratory Efficacy Endpoints

The following subgroups will be included in this study for primary and selected secondary and efficacy endpoints: stratification factors (patients with RHC available at baseline and post bronchodilator FEV1/FVC ratio below/above 0.8), younger versus elderly, gender, etc.

Details of subgroup analyses will be given in the Statistical Analysis Plan (SAP).

All biomarker analyses will be of exploratory nature and be descriptive only.

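### Randomisation is stratified by previous RHC and FEV1/FVC, but the primary test is fixed as an unstratified chi-square; a CMH test over the same strata would hold alpha at 5% and add about 0 to 3 points of power if the factors are prognostic

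*Protocol*

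**What the plan says.** Section 4.2 states that "the randomization will be stratified by availability of a previous RHC (yes/no) and by FEV1/FVC ratio below/above 0.8"; Sections 3.1 and 3.3.6 name the same two factors. Besides balance between arms and protection against selection bias, Section 3.3.6 gives a prognostic reason: "Stratified randomization is included as the treatment outcome may be affected by these factors".

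For the primary endpoint, Section 6.4.1 says the analysis "will compare disease progression rates in each treatment arm using a Chi-square test with a one-sided significance level" of 0.05. The Synopsis (Statistical Methods, Primary Analysis) repeats that the analysis of the "primary endpoint will compare disease progression rates in each treatment arm using a Chi-square test". Both places leave the details of the sensitivity analyses to the SAP, but they state the primary test outright.

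The only analysis role the protocol gives the two factors is as subgroups (Section 6.4.3).

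**The concern.** Stratified allocation balances the two factors between arms. If they predict progression, the true sampling variance of the difference in proportions is smaller than the variance the crude chi-square uses, because the crude variance still contains the variation between strata. The test then rejects less often than 5% under the null and gives up some power under the alternative. An analysis over the randomisation strata removes that excess variance at no cost in patients.

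Only efficiency is at stake. Type I error is not inflated, and power does not fall below plan. The SAP cannot settle the point by itself, since a SAP naming a stratified primary test would contradict the protocol.

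**Working it through.** **1. The plan's own figure.** Inputs from Section 6.1: p1 = 0.72, p2 = 0.54, one-sided alpha 0.05, power 80%, 1:1 allocation, total 176. With pooled variance, no continuity correction and mean rate 0.63:

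n per arm = [1.645 × √(2 × 0.63 × 0.37) + 0.842 × √(0.72 × 0.28 + 0.54 × 0.46)]² / 0.18²
= [1.645 × 0.6828 + 0.842 × 0.6708]² / 0.0324 ≈ 87.9, so 88 per arm and 176 in total.

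Analytic power at 88 per arm is 80.04%. The stated sample size is therefore exactly right for the crude one-sided test.

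**2. Why the crude test is conservative.** The crude variance is proportional to p(1 − p). With balanced strata the relevant variance is the average of p_s(1 − p_s) over strata s.

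As an illustration, take RHC-yes in 20%, FEV1/FVC below 0.8 in 30%, independent factors, and an odds ratio of 3 for each. With 72% overall, the stratum rates are about 0.62, 0.83, 0.83 and 0.94, with shares 0.56, 0.24, 0.14 and 0.06.

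- Within-stratum average: 0.56 × 0.2356 + 0.38 × 0.1411 + 0.06 × 0.0564 ≈ 0.189.
- Crude: 0.72 × 0.28 = 0.2016.
- Ratio ≈ 0.937, square root ≈ 0.968. The effective critical value is 1.645 / 0.968 ≈ 1.70, so true one-sided alpha is about 4.5%. The simulation below gives 4.47% for this case.

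**3. Size of the gain.** The protocol gives neither stratum shares nor progression rates by stratum, so both were varied. The only guide is the amendment rationale for Section 1.3, which says RHC results "will be available only in small proportion of patients (majority of the patients so far being eligible are based on ECHO data".

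Set-up: 200,000 trials per scenario; N = 176; permuted blocks of 4 within four strata (block size assumed); logistic stratum effects calibrated to 72% and 54% overall, or 72% in both arms under the null; pooled z against CMH, no continuity correction, critical value 1.645. Monte Carlo standard error is about 0.05 points for alpha and 0.09 for power.

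Grid A: RHC-yes 10%, 15% or 30%; ratio below 0.8 in 35% or 50%. Grid B: (RHC-yes, ratio below 0.8) of (20%, 20%), (20%, 30%), (30%, 50%) and (50%, 50%).

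| Odds ratio, each factor | CMH minus chi-square power, A | Chi-square alpha, A | CMH minus chi-square power, B | Chi-square alpha, B |
|---|---|---|---|---|
| 1 | -0.3 to -0.2 | 5.0–5.1% | -0.2 | 5.0% |
| 1.5 | about 0 | 4.9–5.0% | 0.0 to +0.1 | 4.9–5.0% |
| 2 | +0.3 to +0.7 | 4.7–4.9% | +0.3 to +0.8 | 4.7–5.0% |
| 3 | +1.3 to +2.0 | 4.3–4.6% | +1.2 to +2.3 | 4.2–4.6% |
| 4 | +2.0 to +3.1 | 3.9–4.4% | +1.9 to +3.5 | 3.7–4.5% |

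With only one factor prognostic at odds ratio 3 (grid A), the gain is +0.8 to +1.1 for FEV1/FVC alone and +0.1 to +0.8 for RHC alone. CMH alpha is 4.9–5.2% in A and 4.9–5.1% in B. It holds even with 10% RHC, where the smallest cell can expect only about 0.10 × 0.35 × 176 ≈ 6 patients. Chi-square power in A stays at 80.3–82.4%.

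**The case against.** The strongest reply is that nothing is wrong. The test is prespecified, valid and correctly powered, and stratified allocation achieves balance and protection against selection bias (Sections 3.3.6 and 4.2) whichever test follows. That stands, and it is why this is an optional improvement.

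Strong prognostic value is also doubtful. Exclusion 7 removes ratios below 0.70, so the lower FEV1/FVC stratum spans only 0.70 to 0.80. The other factor is whether a previous RHC was available, not a haemodynamic value. In grid A, a gain of 3 points needs odds ratios of 4 on both factors, 30% with RHC and an even FEV1/FVC split. This stands too: with a small RHC share, odds ratios of 2 give roughly half a point or less.

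The simulation assumes a common treatment odds ratio. If the log odds effect above 0.8 is half that below it (10% RHC, 35% below 0.8), the change is -0.3 points at odds ratio 1.5 and 0.0 at 2. The reverse pattern gives +0.2 and +0.8. The sign can therefore vary, but the possible loss stays at a few tenths of a point.

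The SAP may already hold a stratified sensitivity analysis. That would leave the primary test, which the protocol fixes, unchanged.

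**Conclusion.** The point holds, at low priority. The primary test does not use the strata that define the randomisation, although the protocol itself says they may affect outcome. The consequence is mild conservatism and some forgone power: nothing or a loss of up to 0.3 points if the factors carry little prognostic information, around 1 to 2 points if each has an odds ratio near 3, and around 2 to 3 points near 4. These figures rest on assumed stratum shares, assumed odds ratios equal for the two factors, a common treatment odds ratio and blocks of 4. The small RHC share points to the lower half of the range. Neither the sample size nor the validity of the planned test is in question.

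**What to change.** In Section 6.4.1 and the Synopsis, make the primary test a one-sided 0.05 CMH test over the four randomisation strata as recorded in the IxRS. Report a stratum-weighted risk difference and name the weights; Mantel-Haenszel weights suit the small cells. Keep the crude chi-square as a sensitivity analysis.

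State which stratum a ratio of exactly 0.8 belongs to, since the current wording covers only below and above. The planned subgroup analysis needs this as well.

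For consistency only, use the same strata for the proportion with 6MWD decline and for the log-rank and Cox analyses. Section 6.4.2 makes this secondary: "For all secondary endpoints p-values will be reported in a descriptive fashion".

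The cost is about one sentence in each of two places, with no added patients, visits or data, and up to 0.3 points of power if neither factor is prognostic under the common-effect assumption. As a protocol amendment it also needs the approvals in Section 9.6, and it should be final before treatment codes are released for the primary analysis.

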4.5.7 GAP Score and Index for IPF

The gender, age and physiology (GAP) score and index for IPF will be automatically calculated based on the information recorded in the eCRF (age, gender, FVC and DLCO).

4.5.8 12-lead Electrocardiograms

Single 12-lead ECG recordings will be obtained at specified timepoints, as outlined in the Schedule of Assessments (see [Appendix 1](#)).

All ECG recordings must be performed using a standard high-quality, high-fidelity digital electrocardiograph machine equipped with computer-based interval measurements. Lead placement should be as consistent as possible.

Patients must have been in a supine or semi-supine position for at least 5 minutes prior to the recording being taken. All ECGs are to be obtained prior to other procedures scheduled at that same time (e.g., vital sign measurements, blood draws) and should not be obtained within 3 hours after any meal. Circumstances that may induce changes in heart rate, including environmental distractions (e.g., television, radio, conversation) should be avoided during the pre-ECG resting period and during ECG recording.

Paper copies of ECG tracings will be kept as part of the patient's permanent study file at the site. The ECG printout must be (1) reviewed by a medically qualified member of the study team at the site, (2) annotated to indicate any clinical finding and (3) dated and signed by this person and filed in the patient notes. ECG parameters will be entered into the eCRF.

If any ECG abnormality is associated with an adverse event, it must be recorded as described in [Section 5.2.1](#).

4.5.9 6-Minute Walk Test and Oxyhemoglobin Saturation

The 6MWT measures the distance that a patient can quickly walk on a flat, hard surface in a period of 6 minutes. Oxyhemoglobin saturation (SpO₂) at rest and during the 6MWT will be assessed at specified timepoints, as outlined in the Schedule of Assessments

(see [Appendix 1](#)). The 6MWT will be performed according to standard procedures ([ATS Statement, 2002](#)) described in the Procedure Manual.

The 6MWT will be performed once for the visits highlighted in the Schedule of Assessments ([Appendix 1](#)). At Day 1, 6MWT will be performed twice and the better of the two 6MWT values will be reported as the baseline value. It is important to remember that for each 6MWT, information on oxyhemoglobin desaturation, Borg scale and O₂ requirements have to be collected.

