6.1 DETERMINATION OF SAMPLE SIZE

There are no reference data available on the use of pirfenidone in this patient population with a measurable DLCO \leq 40% of predicated value and mPAP \geq 20 mmHg on RHC. A total sample size of approximately 176 patients is planned, and patients will be randomized 1:1 to the two treatment groups. The statistical hypothesis for the treatment comparison is based on the proportion of patients who experienced a \geq 15% decline from baseline in 6MWD, were hospitalized for cardiac- or respiratory non-elective reasons, or who died, according to a pooled analysis of the effects observed in the pirfenidone groups of three large Phase III trials (CAPACITY 1, CAPACITY 2, and ASCEND).

The planned sample size is based on the primary endpoint, proportion of patients with disease progression and assumes 80% power and a one-sided significance level of 5%. Given the disease progression rate of 72% by 52 weeks in the three large registration trials for pirfenidone, and assuming an additive effect of sildenafil on pirfenidone, a disease progression rate of 54% in the combination treatment group is assumed and an absolute difference of 18% (respectively a relative reduction of 25%) in disease progression rates is considered a clinically meaningful treatment benefit.

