6.4.2 Secondary Efficacy Endpoints

The secondary efficacy objective for this study is to evaluate the efficacy of adding sildenafil compared with placebo to pirfenidone treatment on the basis of the following endpoints:

- Progression-free survival, defined as time to decline in 6MWD of $\geq 15\%$ compared with baseline (as defined above), respiratory-related non-elective hospitalization, or death from any cause will be analyzed using Kaplan-Meier techniques and the two treatment arms will be compared with a log-rank test. In addition, hazard ratios and corresponding 95% CI will be calculated by applying Cox-proportional hazard models.
- The proportion of patients with decline in 6MWD of $\geq 15\%$ from baseline (as defined above), will be compared using a Chi-square test with a one-sided significance level $\alpha=0.05$. The change in 6MWD from baseline to 12 months will be analyzed using a rank ANCOVA model with the 6MWD recorded at 12 months as the outcome variable and standardized rank baseline 6MWD as a covariate.
- Respiratory-related non-elective hospitalization, all-cause mortality, all-cause non-elective hospitalization and respiratory-related mortality will be analyzed using Kaplan-Meier techniques and the two treatment arms will be compared with a log-rank test. In addition, hazard ratios and corresponding 95% CI will be calculated by applying Cox-proportional hazard models.
- Changes from Baseline to End of Treatment for the following ECHO parameters:
 - Peak tricuspid regurgitation velocity (m/s)
 - PAPs

Pulmonary function tests (PFTs), i.e., FVC, FEV1, FEV1/FVC, and DLCO will be analyzed in terms of absolute mean changes from baseline to week 52 of treatment in actual and % of predicted values. In addition, 5% and 10% categorical changes from baseline will be summarized descriptively. The change from baseline for all

aforementioned parameters will be compared between the treatment arms using a rank ANCOVA with change from baseline as outcome variable and standardized rank baseline value as covariate.

- Oxyhemoglobin saturation (SpO₂) at rest and during the 6MWD will be summarized descriptively over time.
- Borg scale measurement of perceived exertion will be summarized descriptively over time.
- Lung transplantation will be analyzed descriptively.
- WHO Functional Class will be summarized descriptively over time.

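### The primary test is fixed as an unadjusted chi-square: valid and correctly powered, but it leaves out the randomisation factors and the baseline 6MWD and DLCO, which could add precision at no extra enrolment

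*Protocol*

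**What the plan says.** Section 6.4.1 states that the primary analysis of the composite endpoint "will compare disease progression rates in each treatment arm using a Chi-square test with a one-sided significance level" of 0.05, in all randomised patients. The synopsis repeats this. No covariate or stratification term is named. Only the sensitivity analyses of the primary endpoint are deferred to the SAP, so the confirmatory test is settled in the protocol.

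Section 6.1 sizes the trial for that test. It "assumes 80% power and a one-sided significance level of 5" per cent. The rates are introduced with "Given the disease progression rate of 72% by 52 weeks in the three large registration trials for pirfenidone" for the control arm, and "a disease progression rate of 54% in the combination treatment group is assumed" for the other. "A total sample size of approximately 176 patients is planned", and "patients will be randomized 1:1 to the two treatment groups".

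Randomisation is stratified by previous RHC and by FEV1/FVC below or above 0.8 (sections 3.1 and 4.2). Section 3.3.6 gives as the reason that these factors may affect outcome. Baseline 6MWD is the better of two Day 1 tests (section 4.5.9). DLCO is scheduled at screening and at Visit 1 (Appendix 1). Section 6.4.2 uses the baseline value as covariate in rank ANCOVAs of 6MWD and of the lung function tests, DLCO included.

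**The concern.** Factors important enough to stratify on, and baseline measures already used as covariates for secondary endpoints, are left out of the one confirmatory comparison. Walk distance and DLCO are not randomisation factors, so they are balanced between arms only by chance.

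Baseline 6MWD may plausibly matter. The walk component is a percentage fall from baseline, and entry allows 100 to 450 m. A 15% fall is therefore 15 m at one end of the range (0.15 × 100) and 67.5 m at the other (0.15 × 450). Unless test-to-test variability scales exactly with baseline, the chance of crossing the threshold depends on where the patient starts. This is inference; the protocol gives no prognostic figure.

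What is at stake is precision. As shown below, the sample size has no spare power. Section 6.1 states no allowance for dropout, and patients who leave are not replaced.

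**Working it through.** **1. The stated sample size.** Inputs from section 6.1: p₁ = 0.72, p₂ = 0.54, difference 0.18, one-sided α = 0.05 (z = 1.645), power 0.80 (z = 0.842). The mean rate is 0.63.

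n per arm = [1.645 × √(2 × 0.63 × 0.37) + 0.842 × √(0.72 × 0.28 + 0.54 × 0.46)]² / 0.18²
= [1.645 × 0.6828 + 0.842 × 0.6708]² / 0.0324
= 1.688² / 0.0324 ≈ 87.9, so 88 per arm and **176 in total**, as stated.

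By the same formula, power at 88 per arm is 80.0% (80.4% by exact calculation). The plan's figure is right for the test it names.

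**2. Chance imbalance.** For a baseline covariate that is not stratified on, the difference between arm means has SD √(2/88) = 0.15 covariate SDs.

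**3. What adjustment would change.** Two simulations, each with 5,000 trials per setting at 88 per arm, compared the chi-square with a logistic model standardised to the marginal risk difference (influence-function standard error), one-sided at 5%. Progression was logit-linear in standard normal covariates, with the marginal rates held at 72% and 54%. One simulation used a single baseline score with log-odds of 0 to 1.4 per SD; the other used two covariates. The strength of prediction, shown as AUC, is an **assumption** in both.

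| Assumed AUC | Covariates | Chi-square power | Adjusted power | Change (points) |
|---|---|---|---|---|
| 0.50 | one | 80.1% | 80.1% | 0.0 |
| 0.50 | two | 80.9% | 80.6% | −0.3 |
| 0.59 | one | 79.4% | 80.1% | 0.7 |
| 0.63 | two | 80.6% | 82.3% | 1.7 |
| 0.64 | one | 80.5% | 82.2% | 1.7 |
| 0.69 | two | 80.9% | 83.8% | 2.9 |
| 0.71 | one | 79.1% | 83.8% | 4.7 |
| 0.74 | two | 81.0% | 86.3% | 5.3 |
| 0.76 | one | 81.2% | 87.6% | 6.4 |
| 0.81 | one | 80.8% | 89.3% | 8.5 |

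The Monte Carlo standard error of each power figure is about √(0.8 × 0.2 / 5000) = 0.6 points, which explains why the chi-square column moves around 80%.

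In the one-score runs the variance of the unadjusted estimate divided by that of the adjusted one was 1.05 at AUC 0.64, 1.13 at 0.71 and 1.32 at 0.81. At AUC 0.71 this is worth about 176 × 1.13 ≈ 199 patients analysed without adjustment.

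**4. Type I error.** With 72% in both arms, the one-score runs rejected in 4.8% to 5.5% of trials for the chi-square and 4.9% to 5.5% for the adjusted test. The two-covariate adjusted test rejected in 5.1%. Both methods hold their level.

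**5. Room for the model.** At the design rates the expected number without progression is 88 × 0.28 + 88 × 0.46 ≈ 65, and with progression about 111. Treatment plus four baseline terms makes five, so the smaller group has about 65 / 5 = 13 patients per term.

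**Limits.** The simulations assume complete outcomes and simple allocation. They do not model the two randomisation factors, so they put no figure on what those factors would add.

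**The case against.** The strongest reply is that nothing here is wrong. The chi-square is valid under randomisation, the sample size was built for it, and preferring a more efficient method is not finding a fault. That stands, and it decides the class of this point. It is also fair that prediction may be weak. Entry restricts DLCO to at most 40% predicted, 6MWD to 100–450 m and WHO class to II–III, and the walk component is already scaled to the patient's own baseline. At an AUC of 0.59 the gain is under one point.

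Four stronger readings are tempting, and the protocol does not support them:

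- *The baseline severity data go unused.* Section 6.4.2 uses baseline 6MWD and baseline lung function, DLCO included, as rank-ANCOVA covariates. Only the GAP score has no named analysis, and that is no defect in itself.
- *The time-to-event analyses are unadjusted too.* The text says only that "hazard ratios and corresponding 95% CI will be calculated by applying Cox-proportional hazard models". It does not exclude covariates, and their choice may properly be left to the SAP.
- *Chance imbalance biases the primary test.* Imbalance is part of the random error that the 5% level already covers. What is lost is precision, and accuracy given the imbalance that happens to occur.
- *The randomisation factors say nothing about prognosis.* Section 3.3.6 says they may affect outcome, which is a reason to put them in the model.

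An adjusted sensitivity analysis may exist in the SAP, which is not at hand. It would not change the confirmatory test that section 6.4.1 fixes.

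**Conclusion.** The point holds as an efficiency improvement. The confirmatory test is fixed without the two randomisation factors and without baseline 6MWD or DLCO, while secondary analyses are adjusted for baseline. The test is valid, and its stated 80% power at 176 patients reproduces exactly.

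The certainty is uneven. That the primary test is unadjusted is plain from the text. The size of the gain is not: it runs from nothing at an AUC of 0.50 to 8 to 9 points of power at 0.81, and the protocol gives no basis for choosing a value in that range. The middle of the range, AUC 0.63 to 0.74, gives about 2 to 5 points. The possible loss is about 0.3 points, within simulation error. The case for change is this asymmetry, not a large assured benefit.

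**What to change.** In section 6.4.1 and the synopsis, before unblinding, make the primary analysis a logistic model with these main effects only:

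- treatment;
- previous RHC (yes/no);
- FEV1/FVC below or above 0.8;
- baseline 6MWD (continuous);
- baseline DLCO % predicted (continuous).

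Standardise the fitted model over all analysed patients to the marginal difference in 52-week progression proportions, with a robust standard error, and test it one-sided at 5%. Keep the chi-square as a supportive analysis.

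Name this one covariate set and leave no choice between DLCO and GAP; GAP already contains DLCO. State which value serves if a baseline measurement is missing. Eligibility requires a measurable DLCO and a 6MWD at screening, so a fallback exists for each. Also state what is done if the model does not converge: the amendment summary expects RHC results in only a small proportion of patients, so that stratum may be thin.

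The cost is one paragraph in an amendment, carried into the SAP. It needs no new data and no more patients, and the treatment effect being estimated stays the difference in 52-week proportions. After unblinding, the same change would carry little weight.
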